management. The other group, named Efficacy Safety Score (ESS) (n=100) will receive care and management according to ESS. In the ESS group, we will assess ESS in parallel with the telemetrically retrieved physiological variables. A randomization of the patients to group SCG and ESS will be done a priori by using a simple block randomization and sequentially numbered opaque sealed envelopes (SNOSE) will be produced. After obtaining patients' consent, the nurses at the ward will pick a sealed opaque envelope with the randomization code enclosed for each patient. This takes place at the ward when the patients are prepared for surgery. The nurses including patients will not have access to the envelopes before time of enrolment. Because of the logistics in this situation, and the fact that it is the ordinary ward staffing which is to perform this, we have concluded that the use of SNOSE is the best allocation concealment we can obtain in this situation. The Regional Medical Ethics Committee recognized two different letters of consent to the SCG and the ESS groups to be the best solution, and to secure correct handling of this, the manual way with sealed envelopes is regarded most robust for this study situation. By this method we plan to reduce selection bias to a minimum. See also enclosed flow-chart.

Hospital setting

We plan to perform the study at the surgical ward 3 at St Olav University Hospital, Orkdal, Norway. The regular nursing staff will be collecting the postoperative data after supervision and education by the PhD-candidate and a dedicated project nurse. The patient population at this ward available for this study will be persons planned for scheduled surgery (bariatric surgery, shoulder joint replacements, knee/hip joint replacement, major abdominal surgery (hemicolectomy e.g.,), robot-assisted radical prostatectomy (RARP)) and acute surgery (orthopaedic ankle and hip surgery, acute abdomen) which is at the hospital staying at least 24 hours after surgery. The number of these patients at Orkdal is 8-12 patients a week. Limitations in the number of monitoring devices (two sets) for the ESS group, will limit the number of patients which can be included each day. Based on this we think that a maximum of 6-8 patients per week is a reasonable goal for inclusion. From this a number of 25-35 effective weeks with inclusion would be reasonable.

Inclusion/Exclusion criteria

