We performed a power analysis based on the sub-group results of a validation study addressing ESS in total 207 patients [11]. Estimates shows that for obtaining a power of 0,8 with alpha cut-off at 0,05 and beta cut-off at 0,2, a sample size of total 130 patients was required to reach a 25% reduction of time until full mobilization (being able to walk one or more steps with/without support). A total sample size of 130 patients was required to reach a 25% reduction in total hospital stay and a total sample size of 506 and 176 patients was required to reach a 25% reduction in pain at rest and at mobilization, respectively. (Kane SP. SampleSizeCalculator. <http://clincalc.com/Stats/SampleSize.aspx>). Except from pain at rest, which is of limited interest in this study, these sample size calculations suggest that a total sample size of 200 (100 in each group) will be sufficient to detect any meaningful effects of the intervention on both primary and secondary outcomes.

Data collection

Patients will be included after giving their informed signed consent. In both groups, a standardized questionnaire (see attachment) focused on postoperative management and satisfaction will be performed 24 hours postoperatively. In group ESS, we will register ESS for the first 24 hours postoperatively. Registration of ESS is to be done hourly for the first four hours, and then every second hour after the patient has arrived to the ward. For all patients the Modified Aldrete Score and the New Early Warning Score [14-16] will be performed for comparison. If ESS>10 in patients of group ESS, the anaesthesiologist on duty might be called upon (not involved in the study) for assistance. He/she will afterwards be asked to evaluate the necessity of the consultation for later sensitivity/specifity test. All the data will be collected by the nurses with the help of a designed program (Patient Status Engine) on tablet PC from Isansys (Isansys Lifecare Ltd., Oxfordshire, UK) that incorporates ESS into their wireless monitoring platform, Patient Status Engine (PSE) which is a CE-approved device (class IIa) designed for use in hospital settings to collect vital parameters. The data is then transferred to a protected data base locally. Statistical analysis will be performed in SPSS.

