Attachment 1:

MAL FOR INTERVJU 1. POSTOPERATIVE DAG

Efficacy Safety Score

Prosjekt nr: _____

Informert samtykke (sett kryss):

Inngrep: _____

Operasjonsdato: _____

1. **Tidspunkt for mobilisering (gå ett eller flere skritt med/uten støtte):** kl _____

2. **Kan du angi verste smerte siden operasjonen (0-10)?** _____

• Hvilken situasjon utløste verste smerte: _____

3. **Kan du angi gjennomsnittlig smerte siden operasjonen (0-10):** _____

4. **Har du opplevd kvalme etter operasjonen?** Ja/Nei

• Hvis Ja, hvor stor andel av tiden: En episode - litt - halvparten - meste - hele tiden

5. **Har du hatt brekninger og/eller oppkast etter operasjonen?** Ja/Nei

6. **Kan du si noe om nattesøvnen etter operasjonen:**

• Mengde: Ingen – redusert – normal – øket – kraftig øket

• Kvalitet: Normal – urolig/mareritt – urolig/smerte – urolig/vonde tanker

7. **Kan du angi eventuell bekymring/engstelse før operasjonen:**

• Ingen – litt – middels – mye – svært mye

8. **Kan du angi eventuell bekymring/engstelse nå etter operasjonen:**

• Ingen – litt – middels – mye – svært mye

9. **Kan du si noe om din følelse av sikkerhet og trygghet etter operasjonen:**

• Sikker og trygg – stort sett sikker/trygg – verken eller - noe usikker/uttrygg – usikker/uttrygg

10. **Kan du angi din evne til å huske, resonnere, ta beslutninger eller følge med etter operasjonen:**

• Normal - litt redusert – redusert - en del redusert - kraftig redusert

11. **Andre plager eller bivirkninger etter operasjonen?** _____

12. **Kan du angi din grad av tilfredshet med behandling etter operasjonen:**

• Meget utilfreds – litt utilfreds – nøytral – tilfreds – meget tilfreds

13. **Eventuelt andre kommentarer/tilbakemeldinger:**

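### The primary endpoint's only stated source is a 24-hour interview form filled in by unblinded ward nurses, who also ask about satisfaction; same-time charting and a sealed satisfaction item would be a cheap improvement

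*Combined protocol and SAP*

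**What the plan says.** **Who collects.** Hospital setting: "The regular nursing staff will be collecting the postoperative data", once trained by the PhD candidate and a project nurse. Data collection repeats this without exception: "All the data will be collected by the nurses with the help of a designed program (Patient Status Engine) on tablet PC".

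**Who knows the arm.** Under Study design, after consent, "the nurses at the ward will pick a sealed opaque envelope with the randomization code enclosed for each patient". Care by ESS is then given on the same ward. The same section reports that the ethics committee "recognized two different letters of consent to the SCG and the ESS groups to be the best solution", so patients probably know their arm too (an inference).

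**How the endpoint is captured.** Data collection describes a questionnaire for both groups, "focused on postoperative management and satisfaction will be performed 24 hours postoperatively". Attachment 1 is that form, headed in Norwegian as a template for an interview on the first postoperative day. Item 1 is a clock-time field: "Tidspunkt for mobilisering (gå ett eller flere skritt med/uten støtte". Item 12 is a five-level rating of satisfaction with treatment after the operation. Primary and secondary endpoints lists time to full mobilisation as primary and satisfaction as secondary.

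**Contact schedule.** For the ESS group, "Registration of ESS is to be done hourly for the first four hours, and then every second hour" after arrival on the ward. The Modified Aldrete Score and an early warning score are done in all patients, with no frequency given.

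**What is not stated.** No other source for mobilisation time, no masked assessor and no self-completion. The protocol discusses selection bias (Study design) and influence of the ESS arm on standard care (Methods of analysis, Data collection), but not bias in outcome assessment.

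**The concern.** Two outcomes pass through staff who know the allocation and belong to the team giving the intervention.

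For the primary endpoint, a time entered a day later is only as good as what it is based on. If one arm has prescribed bedside contacts around the time of first steps and the other has none stated, the entered times may differ in accuracy, or in systematic error, between arms. A shift of that kind goes straight into the treatment comparison, and a larger sample does not dilute it.

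For satisfaction, patients are asked face to face, by staff of the ward whose care they are rating, in an open-label trial of a nurse-delivered tool. Courtesy answers may differ by arm for reasons other than the care received.

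**Working it through.** **1. Is there another source for the event time?** Hospital setting and Data collection assign all data to the nurses. Attachment 1 item 1 holds the mobilisation time. Table 1 (ESS) scores mental status, nausea and vomiting, pain at rest and on movement, and general condition; it has no walking item. Item 1 is therefore the only stated source. No sentence names the interviewer; that it is a ward nurse follows from the two staffing statements.

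**2. Recall or notes?** Most later items are worded as questions to the patient. Item 1 is a bare field. The form fits either reading, and no chart source is named.

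**3. Contacts by arm.** ESS readings over a full 24 hours from ward arrival: 4 + (24 − 4)/2 = 14, an upper limit because registration covers the first 24 hours after surgery and some of those precede arrival. Only contacts before first steps bear on the timing. If first steps came 8 to 12 hours after arrival (assumed), that is 4 + (8 − 4)/2 = 6 to 4 + (12 − 4)/2 = 8. For standard care the number is unknown.

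**4. The plan's own figure.** Sample size gives a total of 130 for a 25% reduction in time to mobilisation, alpha 0.05 and power 0.80, without a mean or SD. Assuming a two-sided comparison of two means with 65 per arm, the implied coefficient of variation is CV = 0.25 × √(65/2) / (1.960 + 0.842) = 0.509. This is solved backwards from 130 and does not verify it; a one-sided test would imply 0.573.

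**5. Illustration only.** Suppose there is no true effect, 100 patients per arm, and standard-care times are recorded late by an assumed lag. With mean time m, d = (lag/m) / (CV × √(2/100)), and the two-sided false-positive probability is Φ(d − 1.96) + Φ(−d − 1.96). At CV 0.509:

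| Assumed lag | Assumed mean | Shift | False-positive probability |
|---|---|---|---|
| none | any | 0% | 5% |
| 15 min | 12 h | 2.1% | 6% |
| 30 min | 12 h | 4.2% | 9% |
| 30 min | 8 h | 6.3% | 14% |
| 60 min | 12 h | 8.3% | 21% |
| 60 min | 8 h | 12.5% | 41% |

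The CV matters as well: for a 10% shift the probability runs from 42% at CV 0.4 to 17% at CV 0.7.

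The plan specifies Kaplan-Meier and Cox analysis, not a test of means. A simulated log-rank test (100 per arm, gamma or lognormal times at CV 0.509, censoring at 24 hours, 6,000 repeats) gave about 8–9% for 30 minutes on 12 hours and 29–32% for 60 minutes on 8 hours.

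If the error were equal in both arms there would be no bias of this kind. If ESS times were the late ones, the bias would run against ESS.

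**6. Satisfaction.** With 100 per arm and an assumed top-category rate of 40–60%, a pure reporting shift of 10 percentage points would be declared significant in about 29–32% of trials. The 10 points are also an assumption.

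**The case against.** A reader might infer that standard-care times rest on patient recall while ESS nurses log the first steps as they occur, and that the false-positive risk is therefore as high as 41%. The documents do not support that. Item 1 is not worded as a question and could be filled from notes. Both arms use the same field on the same form. No text says that an ESS visit records walking. Standard-care patients also have nurse-recorded scores, at an unstated frequency. A lag of 30–60 minutes, in one arm and one direction only, has no basis in the protocol; the CV is back-solved; and 41% comes from a test of means that is not the planned analysis. All of this stands, so no figure in the illustration should be read as an estimate.

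A second objection is that the remedy is partial. A nurse who is absent at first steps cannot chart them at the time. The charting nurse still knows the arm and can still influence when the patient is mobilised. This also stands. Entries made at a later contact need to be marked, and the claim must be limited to reduction.

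A third is that moving the pain items to a written form would change the mode of a secondary endpoint that the protocol defines on a verbal numeric scale. That is right, and pain should stay verbal.

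The objections do not dispose of the point. If the protocol is followed as written, unblinded ward staff take satisfaction answers in person and enter the primary event time on a 24-hour form with no specified basis.

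**Conclusion.** The point holds as a cheap improvement to measurement. It does not demonstrate bias. What is established is that the primary endpoint has one stated source, a 24-hour interview form completed by staff who know the arm; that the basis for its entry is unspecified; that only one arm has a stated contact schedule; and that satisfaction is asked by staff of the ward under evaluation. Differential error is therefore possible, but its size and direction cannot be computed from the documents.

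The verdict rests on two inferences: that the interviewer is a ward nurse, and that the ward team as a whole knows the allocation. It does not require that the individual interviewer gave the care being rated.

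**What to change.** 1. Reconcile the event definition. The endpoint section requires more than a single step, whereas Sample size and Attachment 1 count a single step as enough.
2. In both arms, staff enter the date and clock time of first steps on the same one-line bedside or tablet record when they happen. If nobody was present, the entry is made at the next contact and marked as such.
3. State that this entry is the source for the primary endpoint, with item 1 of the 24-hour form as back-up only. Report by arm how many times were charted at the event, charted later, or taken from the back-up.
4. Patients complete the satisfaction item themselves and return it in a closed envelope. Pain stays on the verbal numeric scale.

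Cost: one extra entry per patient, a small change to an existing form, and some blank satisfaction items. Nurses already collect all the data, so no added staff should be needed, although the protocol does not say so. The charting nurses, and probably the patients, remain unblinded, and that limit should be acknowledged in the protocol.

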Inclusion criteria: all subsequent patients undergoing surgery that expectedly will be treated and observed in hospital for more than 24 hours postoperatively. Exclusion criteria: patients < 18 years of age, refusal of participation, poor communication capabilities and surgery performed that is not compatible with anticipated mobilization during the first 24 postoperative hours.

Primary and secondary endpoints

Primary endpoint of this study will be time to full mobilization of the patient, defined as being able to walk more than one step with/without support. Secondary endpoints will be clinically significant reduction (more than 23% [16]) in measured pain evaluated by a 0-10 scale (Verbal Numeric Rating Scale), significant changes in doses (OMEQ) of postoperative administered opioids, re-admissions to the recovery unit, significant increased patient satisfaction of treatment given and reduction in length of hospital stay.

Methods of analysis

Descriptive statistics will be used to compare baseline characteristics between groups, such as type of surgery, type of anaesthesia, regular pain medication, age, relevant comorbidity (Charlson Comorbidity Index), ASA-classification and body mass index. The effect of ESS on the primary outcome (time to mobilization) will be analysed by Kaplan-Meier estimators, and we will also use Cox-regression analysis to adjust for baseline covariates. For the secondary outcomes, we will use linear and logistic regression to estimate differences in means or odds ratios between study groups, depending on the measurement scale. Non-normally distributed variables will be log transformed, or analysed using non-parametric tests. The precision of all estimated effects will be given by a 95% confidence interval. Due to the anticipated positive influence from the ESS group on

postoperative treatment to the SCG, we will also see if there is a progression in eventually differences in the endpoints between the SCG and ESS group.

Sample size

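### Patients who could not walk even before the current illness or injury are eligible, cannot reach the walking endpoint, and so cost the trial power

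*Combined protocol and SAP*

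**What the plan says.** The section on endpoints states (final word, on support, omitted): "Primary endpoint of this study will be time to full mobilization of the patient, defined as being able to walk more than one step with/without".

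Under Inclusion/Exclusion criteria, the trial takes "all subsequent patients undergoing surgery that expectedly will be treated and observed in hospital for more than 24 hours postoperatively". The exclusions are age under 18, refusal, poor communication, and "surgery performed that is not compatible with anticipated mobilization during the first 24 postoperative hours". Hospital setting lists elective operations and also "acute surgery (orthopaedic ankle and hip surgery, acute abdomen").

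Under Methods of analysis, the primary outcome "will be analysed by Kaplan-Meier estimators, and we will also use Cox-regression analysis to adjust for baseline covariates". The baseline characteristics named there, as examples, are "type of surgery, type of anaesthesia, regular pain medication, age, relevant comorbidity (Charlson Comorbidity Index), ASA-classification and body mass index". Walking ability before admission is not among them.

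The Sample size section states that "a sample size of total 130 patients was required to reach a 25% reduction of time until full mobilization", with 200 to be enrolled. Data collection and Attachment 1 place the recording of mobilisation time in the interview 24 hours after surgery. No censoring rule is given for patients who have not walked. The exclusions after randomisation cover cancelled operations and transfers only.

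**The concern.** The mobility exclusion describes the surgery, not the person. An adult who has long been unable to take a supported step, and who has a hemicolectomy or an operation for acute abdomen, passes every criterion as written. Whatever care is given, that patient has no event.

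Nothing later in the plan deals with this. The patient stays at risk until censored, in whichever arm the envelope dictates, and gives both curves a plateau that has nothing to do with ESS. The planning figure of a 25% shorter time to mobilisation also presumes that every patient has such a time. At stake is the chance of detecting a real effect among patients who can walk.

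**Working it through.** **1. The plan's own figure.** The protocol gives a 25% reduction, alpha 0.05, power 0.80 and a total of 130, but no mean, SD or event rate. The 130 can therefore be back-solved but not verified. For two means with 1:1 allocation, taking alpha as two-sided:

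n per arm = 2 × (1.960 + 0.842)² × (SD/mean)² / 0.25²

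Setting n = 65 gives SD/mean = 0.25 × √(65/2) / 2.802 = 0.509. Setting n = 64 gives 0.505. Any ratio between these rounds up to 65 per arm, or 130 in total. Reading the 25% as a hazard ratio of 0.75 does not give 130: the Schoenfeld formula needs 4 × 2.802² / (ln 0.75)² = 380 events.

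**2. Event-time model.** A Weibull distribution with SD/mean of about 0.51 has shape about 2.06. Times multiplied by 0.75 then correspond to a hazard ratio for walking of (1/0.75)^2.06 = 1.81.

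**3. Effect of a fraction f who can never walk.** In each arm S(t) = f + (1 − f) × S_w(t), where S_w is the curve for walkers. The gap between arms therefore shrinks by the factor (1 − f). The largest gap is 0.215 at f = 0, 0.211 at 2%, 0.204 at 5% and 0.193 at 10%.

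Power falls faster than the gap because non-walkers never leave the risk set. Take 100 patients in an arm, 5 of them non-walkers. When 90% of the 95 walkers have walked, 9.5 walkers remain, and non-walkers make up 5/14.5 = 34% of those at risk. The faster arm reaches that state sooner, so its apparent event rate drops first and the hazard ratio is pulled towards 1.

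**4. Power.** Simulated log-rank test (the plan names no test; log-rank is assumed), 100 per arm, shape 2.06, ESS times × 0.75, two-sided 5%. The values of f and the three follow-up rules are assumptions.

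| Non-walkers (of 200) | Full follow-up | Censored when 95% of control walkers have walked | Censored at 85% |
|---|---|---|---|
| 0 | 98% | 98% | 98% |
| 2% (4) | 90% | 94% | 96% |
| 5% (10) | 78% | 86% | 91% |
| 10% (20) | 58% | 70% | 80% |

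Repeat runs agree within about two points. At 1% (2 patients), power is about 95-97%.

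**5. Hazard ratio and the margin in sample size.** A companion simulation used SD/mean 0.507, an assumed control median of 12 hours, and censoring at 24 or 168 hours. With 200 patients the estimated hazard ratio fell from about 1.82 with no non-walkers to 1.69-1.63 at 2%, 1.59-1.51 at 5% and 1.47-1.39 at 10%. With 130 patients and no non-walkers, power was about 90-92%; with 200 patients and 5% non-walkers it was 79-88%. In those settings, keeping ten non-walkers costs more power than enrolling 70 fewer patients.

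**The case against.** The strongest reply is about size. The documents give no share of non-walkers, and nothing in them shows that 5% or 10% is realistic for this ward. Much of the listed surgery is elective, and the communication and surgery-type exclusions plus written consent may narrow the group further. At 1-2%, power stays at about 90% or more, above the planned 80%. This stands.

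Follow-up is the second reply. The 78% and 58% figures need follow-up until every walker has walked, whereas the protocol describes recording mobilisation time only at the 24-hour interview. Earlier censoring softens the loss. This also stands, and is why a range is given.

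A third reply is that 200 exceeds the required 130, so losing ten patients is harmless. This does not hold as put: the ten are not removed but remain at risk throughout, which costs more than their absence would.

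A fourth is that the list of baseline characteristics is open, so walking ability could be recorded and handled in the analysis. That is possible. A stratum of non-walkers has no events and contributes nothing to a stratified log-rank or Cox analysis. The plan does not provide for it, however, and the unadjusted Kaplan-Meier comparison would stay diluted.

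Two stronger readings are tempting. A reader might infer that anyone unable to walk just before surgery can never have the event. The documents do not support this: the threshold is very low and allows support, and a patient immobilised only by a fresh hip or ankle injury, or by an acute abdomen, may take supported steps afterwards. A reader might also infer bias towards ESS. Randomisation spreads non-walkers over both arms in expectation, so the expected error is conservative, although chance imbalance in a single trial could move the curves either way.

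**Conclusion.** The gap in the criteria is real. It is confined to patients who could not walk, even with support, before the current illness or injury. They are eligible, cannot reach the endpoint, and lower the power of the primary comparison.

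The direction is clear; the amount is not known. It rests on an assumed share of 2-10%, a 25% effect confined to walkers, the variability implied by the total of 130, and the follow-up rule. If event times were more variable than that total implies, the starting power would also be lower: with exponential times and follow-up to 168 hours it is about 51% with no such patients and 29% at 5%. It would be wrong to report the trial as underpowered on this ground, since a share of 1-2% leaves power at about 90% or more under the main assumptions. The case for acting is that the potential loss is material and the remedy very cheap.

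**What to change.** Add one exclusion criterion: unable to walk, with or without support, before the current illness or injury. Settle it by a question to the patient or a look at the record, before the envelope is opened, so that it cannot depend on allocation. Dating it to before the current illness or injury keeps patients immobilised only by the acute condition in the trial, whether orthopaedic or abdominal.

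State also how patients who have not walked by the end of follow-up are censored, and when that is.

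If the sponsor prefers to keep intake fully open, the alternative is to record prior walking ability at enrolment and stratify the primary analysis by it. Those patients would then count towards the 200 without contributing to the comparison.

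The cost of the exclusion is one enrolment question, a few patients lost, and a result that does not apply to permanent non-walkers, about whom this endpoint says nothing in any case.

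### The plan names no covariates for the secondary outcomes despite seven kinds of surgery and no strata; adjusting the linear models for type of surgery and regular pain medication would gain precision at almost no cost.

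*Combined protocol and SAP*

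**What the plan says.** **Analysis.** Methods of analysis plans Kaplan-Meier estimation for the primary outcome, plus Cox regression adjusted for baseline covariates. The next sentence covers everything else: "For the secondary outcomes, we will use linear and logistic regression to estimate differences in means or odds ratios between study groups", with the choice depending on the scale of measurement. It names no covariate. Variables that are not normally distributed are to be log transformed or tested non-parametrically.

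**Baseline variables.** The same section compares the groups descriptively on characteristics "such as type of surgery, type of anaesthesia, regular pain medication, age", comorbidity, ASA class and body mass index.

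**Case mix and allocation.** Hospital setting lists five kinds of scheduled operation ("bariatric surgery, shoulder joint replacements, knee/hip joint replacement, major abdominal surgery" and robot-assisted prostatectomy) and two acute ones (ankle and hip orthopaedics, acute abdomen). Study design describes "simple block randomization" and names no strata.

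**Size.** Sample size sets 100 patients per group and concludes that this suffices for the primary and secondary outcomes, apart from pain at rest, which it treats as of limited interest.

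**The concern.** Pain, opioid use and length of stay can be expected to differ between, say, bariatric surgery, joint replacement and an acute abdomen. That is a reasoned expectation; the documents give no figure for it. Where neither the randomization nor the model accounts for type of surgery, those differences stay in the residual variance and widen the interval for the group difference.

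The plan leaves open whether its secondary models do account for it. If they do not, precision is lost although the variables are already recorded. If they might, the choice of covariates stays open until the data are seen. Either way, one sentence of pre-specification is missing, and it matters for outcomes on which the plan claims adequate power.

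**Working it through.** **Inputs**
- Power and alpha: "for obtaining a power of 0,8 with alpha cut-off at 0,05 and beta cut-off at 0,2" (Sample size). Sidedness is not stated; two-sided is assumed.
- Hospital stay: "A total sample size of 130 patients was required to reach a 25% reduction in total hospital stay".
- Pain: "a total sample size of 506 and 176 patients was required to reach a 25% reduction in pain at rest and at mobilization, respectively".
- Planned size: 100 per group.
- Means and SDs are not printed. Only the source is named: "We performed a power analysis based on the sub-group results of a validation study addressing ESS in total 207 patients".
- Share of variance explained by the covariates (R²): not given; assumed 0 to 0.4.

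**Step 1. Spread implied by the plan's own sample sizes.** For two means with n per group, the standardized effect at 80% power is d = (1.960 + 0.842) × √(2/n). With a 25% reduction, SD/mean = 0.25/d.

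| Outcome | Total N | d | SD/mean |
|---|---|---|---|
| Hospital stay | 130 | 2.802 × √(2/65) = 0.491 | 0.51 |
| Pain at mobilization | 176 | 2.802 × √(2/88) = 0.422 | 0.59 |
| Pain at rest | 506 | 2.802 × √(2/253) = 0.249 | 1.00 |

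Putting these back returns 130, 176 and 506 by construction. This checks consistency; it is not an independent reproduction.

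**Step 2. Unadjusted power at 100 per group.** The non-centrality is d × √(100/2), with a t reference on 198 degrees of freedom.
- Pain at mobilization, 25% reduction: 0.422 × 7.071 = 2.99; power 84.4% (normal approximation 84.8%).
- Pain at mobilization, 23% reduction: d = 0.23/0.592 = 0.389; non-centrality 2.75; power 78.1%. Primary and secondary endpoints uses 23% as its threshold for a clinically significant reduction in pain; it is read here as a reduction in the mean.
- Hospital stay, 25% reduction: 0.491 × 7.071 = 3.47; power 93.3%.
- Pain at rest, 25% reduction: 0.249 × 7.071 = 1.76; power 41.8%.

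**Step 3. Adjusted analysis.** The residual SD is multiplied by √(1 − R²), which is equivalent to 200/(1 − R²) patients. Seven extra coefficients (six for surgery, one for medication) inflate the variance by about 1 + 7/190 = 1.037, so the interval widens by a factor of 1.018, and leave 191 degrees of freedom. The power columns include this penalty.

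| R² | CI width ratio, no penalty | With penalty | Equivalent N, no penalty | Pain at mobilization, 25% | Pain at mobilization, 23% | Stay, 25% |
|---|---|---|---|---|---|---|
| 0 | 1.000 | 1.018 | 200 | 83.1% | 76.6% | 92.4% |
| 0.1 | 0.949 | 0.966 | 222 | 87% | 81% | 95% |
| 0.2 | 0.894 | 0.911 | 250 | 90% | 85% | 97% |
| 0.3 | 0.837 | 0.852 | 286 | 94% | 89% | 98% |
| 0.4 | 0.775 | 0.789 | 333 | 97% | 93% | 99% |

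Adjustment breaks even when (1 − R²) × 1.037 = 1, that is at R² of about 4%.

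**Step 4. Simulation check.** With 200 patients, seven surgery types, blocks of four and no strata (mix and block size assumed), interval-width ratios were 1.018, 0.967, 0.911, 0.852 and 0.788 for R² of 0 to 0.4, matching the penalized column. Adjusted power for pain at mobilization was 84.1, 86.9, 89.9, 94.1 and 96.2%. In a separate simulation under no effect, rejection was 5.2% unadjusted and 5.0% adjusted.

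**Step 5. Logistic models behave differently.** In simulation with a common outcome, adding surgery type and medication raised power (70% to 73% with moderate surgery effects, 50% to 62% with strong ones). The standard error of the log odds ratio grew, however (0.289 to 0.324; 0.287 to 0.375), because the adjusted odds ratio is a conditional quantity. At an assumed event rate of about 5%, the seven-type model was usable in only 158 of 1,000 simulated trials.

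**The case against.** The strongest reply is that the plan is silent rather than wrong. It does not say that the secondary models contain study group alone. The preceding sentence plans adjustment, and regression is the tool that allows it. That stands: a reader might infer a plan for unadjusted models, but the text supports only that adjustment is not stated. The reply does not remove the need to say which covariates enter.

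Second, the unadjusted analysis is valid. Chance imbalance in case mix is already reflected in its confidence interval, and type I error is held. This stands in full.

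Third, the gain is modest where the plan is well powered, and it rests on an R² nobody has shown. Hospital stay is already at about 93%, and pain at mobilization at about 84% for the planned effect. At R² of 10% the gain there is about 3 points. This also stands, although break-even is low, and at the 23% threshold unadjusted power is just under 80%.

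Fourth, adjusting is not literally free, and a remedy confined to linear models would miss the plan's log-transform and non-parametric route. Both are correct, and the fix allows for them.

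**Conclusion.** The point holds as a matter of efficiency and pre-specification for the continuous secondary outcomes: pain, OMEQ and length of stay. For an assumed R² of 10-40%, intervals are about 5-23% narrower before the degrees-of-freedom loss and about 3-21% narrower after it. Power for pain at mobilization rises from about 84% to 87-97% (25% reduction) and from about 78% to 81-93% (23%, read as a mean reduction). For hospital stay the benefit is mainly precision. If R² is zero, adjusting costs 1 to 1.5 points.

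These figures rest on the spread implied by the plan's own sample sizes, a two-sided 5% test, all 200 patients analysed, and the assumed R².

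Three stronger readings are tempting and not supported:
- **That the secondary comparisons are biased.** Randomization keeps them valid.
- **That the secondary outcomes are badly underpowered.** The low figure, about 42%, belongs to pain at rest, which the plan sets aside. It cannot be carried over to opioid dose, for which no spread is given.
- **That adjustment sharpens every secondary result.** It does not narrow odds-ratio intervals.

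**What to change.** In Methods of analysis, state that:
- The linear regressions for pain, OMEQ and length of stay, on the log scale where transformed, include study group and type of surgery, with sparse types grouped and acute and scheduled surgery kept apart. For pain and OMEQ they also include regular pain medication.
- The adjusted estimate is the reported result, with the unadjusted estimate beside it.
- For skewed outcomes, the adjusted log-scale model is preferred to an unadjusted non-parametric test.
- Type of anaesthesia is not a covariate. It is given after the envelope is opened, although the plan lists it among the baseline characteristics.
- Rare binary outcomes such as re-admission to the recovery unit are analysed with study group only, or study group plus acute versus scheduled. No claim of narrower odds-ratio intervals is made.

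The cost is a few sentences of text and about 6-8 of 198 degrees of freedom. The variables are already in the plan, so no extra patients or procedures are needed.
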